Impulsivity: Impulsivity measures will be administered via study laptops in a quiet laboratory testing room at the following time points: baseline and 6, 12, and 24 months after surgery. All tasks are programmed in E-Prime 2.0 (Psychology Software Tools, Inc.). Total administration time is approximately 25 minutes. The tasks are: Stop Signal Task (SST)117: measure of response inhibition which has been used in previous studies of smoking behavior118-120 and obesity.71,72 In this task, participants respond to left and right-facing arrows (go signal) on the computer screen. On 25% of trials, a stop signal (an 800-Hz, 100-ms, 70-dB tone) is presented indicating that the participant should inhibit a response. The initial stop delay in each block is 250ms and adjusts ±50ms depending on whether the participant successfully inhibits.117 Participants complete three 64-trial task blocks. Trials consist of a 500-ms warning stimulus, a 1,000-ms go signal, and 1,000-ms blank screen inter-trial interval. Task duration is approximately 10 min. The primary outcome is stop signal reaction time (SSRT), calculated as the mean RT on go-trials (MRT) minus mean stop delay (MSD). Stroop Test: measure of interference control, or the ability to suppress habitual responses.121 Higher Stroop interference scores are associated with obesity122,123 and disinhibition as assessed by this subscale of the Eating Inventory.124 Participants view a series of words on a computer monitor and using the keyboard, are asked to press the key associated with the color of the word rather than the word itself. Congruent trials are trials in which the word and color match (e.g., the word green appears in the color green). Incongruent trials are trials in which, the words are printed in colors that do not match the colors of the words (e.g., the word "red" might appear in green). Correct responses and reaction time (RT) for congruent and incongruent trials are recorded. The primary outcome is the interference score, which is also calculated as RT(incongruent) minus RT(congruent) and measures the ability to suppress a habitual response in favor of an unusual one, taking into account overall speed of naming. Delay Discounting Task (DDT): participants choose between a smaller reward available immediately (e.g., \$20 today) and a larger reward available after a longer delay (e.g., \$40 in a month). People differ in their degree of delay discounting, the extent to which they forgo larger monetary magnitudes in the future in order to obtain immediate rewards. As in previous work, the immediate reward will be fixed and the magnitude and delay of the larger, later reward will vary from trial to trial. Participants will make 51 choices. The primary outcome will be the subjects discount rate, which will be estimated by fitting a logistic regression that assumes a persons decisions are a stochastic function of the difference in subjective value between the two options.127 Keeping with standard behavioral findings128,129 we will assume that subjective value (SV) is a hyperbolic function of the reward amount (A) and delay (D): SV = A/(1)+kD), where k is the participants discount rate. Larger values of k indicate a greater degree of discounting future rewards. A composite measure of impulsivity will be calculated by averaging individual z-scores derived from the SST, Stroop interference score, and k-value. We predict that higher levels of impulsivity indicating poor response inhibition and greater discounting of future rewards (i.e., slower SST, higher Stroop interference score, and higher k-values) will be associated with less weight loss 24 months following bariatric surgery. Psychopathology: Psychopathology measures will be

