however, are not universal and vary between patients and across surgical procedures. It is estimated that 20-30% of patients experience suboptimal weight loss or significant weight regain within the first few postoperative years. Reasons for this are not fully understood, but likely involve both physiological processes and behavioral factors (e.g., difficulty adhering to the dietary and physical activity recommendations made prior to surgery). Extreme Obesity More than one-third of American adults are obese, defined by a body mass index (BMI) of 30 kg/m2.1 Furthermore, 8.3% of women and 4.4% of men are extremely obese, defined by a BMI 40 kg/m2.1 Obesity, and extreme obesity in particular, is associated with major health complications including coronary heart disease, hypertension, type 2 diabetes mellitus, sleep apnea, and osteoarthritis.2-4 Surgical Treatment of Extreme Obesity Bariatric surgery is currently recommended for individuals 18 years and older with a BMI of 40 kg/m2 or those with a BMI of 35 kg/m2 in the presence of significant co-morbidities.5,6 Approximately 200,000 individuals are estimated to undergo bariatric surgery in the United States each year. The most common surgical procedures include the gastric bypass (GB), sleeve gastrectomy (SG), and adjustable gastric banding (AGB).7,8 As of 2013, the GB was the most common procedure in the United States, comprising 56% of all procedures; the SG comprised 36.3%.8 Anecdotal reports suggest that the SG is increasing in popularity while the AGB is now performed infrequently. With all three procedures, patients typically reach their maximum weight loss of 20-35% of body weight 12 months after surgery.3,4,9-16 These weight losses are associated with significant improvements in obesity-related co-morbidities and decreased risk of mortality.3,4,11,17-24 Despite these impressive results, studies have found that approximately 25% of patients who undergo bariatric surgery fail to reach or maintain the expected postoperative weight loss.25-27 Courcolous and colleagues, for example, observed that 23.6% of GB patients regained weight between postoperative year 1 and year 2. Less is known about the typical postoperative weight trajectory of patient who have undergone SG. Recent studies have suggested that weight regain is associated with deterioration of many of the health benefits seen with bariatric surgery.12,28-31 Psychosocial Status and Psychopathology in Candidates for Bariatric Surgery Extreme obesity is associated with a significant psychosocial burden, including impairments in quality of life, body image, sexual behavior and other areas of psychosocial functioning.32 While this distress is believed to contribute to the decision to have bariatric surgery, its impact on postoperative outcomes is less clear. At present, little is known about the physiological and behavioral contributions to success or failure of bariatric surgery.33 Regardless, weight regain after bariatric surgery is frequently attributed to preoperative psychosocial and behavioral factors.27,34-41 More specifically, there has been a great deal of interest in the presence of formal psychopathology in bariatric surgery patients and its potential contribution to postoperative outcomes.42-45 At least six studies have described rates of psychopathology in candidates for bariatric surgery using structured diagnostic instruments.46-51 Lifetime rates of any psychiatric diagnoses ranged from 36.8%-72.6%, higher than those reported in most studies of the general population. Mood disorders were the most frequent diagnoses, seen in 22.0%-54.8% of patients. Substance use disorders (SUDs) were found in up to 35.7% of patients and alcohol abuse or dependence in up to 33.2%. Binge eating disorder (BED), defined as eating an unusually large amount of food within a short period of time coupled with a loss of control over eating, has been diagnosed in 4.6% to 27.1% of patients. Current diagnoses (as compared with lifetime) were less common, reported in 20.9%-55.5% of candidates for surgery. Mood disorders were diagnosed in up to 31.5%. BED ranged from 3.4%-41.9%. Current substance use was seen in less than 2% of patients. (Note. The lower percentages of those with current psychopathology, as opposed to lifetime psychopathology, are expected.) While studies of the psychosocial characteristics of bariatric surgery candidates have been informative, they are not without limitations. Many studies have suffered from methodological concerns, including small sample sizes or lack of an appropriate comparison group. Further, establishing psychiatric diagnoses prior to bariatric surgery is challenging. Perioperative guidelines suggest that patients undergo an evaluation with a mental health professional prior to surgery3 and most third party payers require these evaluations. However, most programs do not use structured clinical interviews to establish diagnoses for clinical purposes.52,53 Several studies have suggested that candidates for bariatric surgery engage in impression management prior to surgery, in which they minimize reports of psychopathology to present themselves to the bariatric team in the most favorable light.54-56 To address this issue, assessment of psychiatric symptoms for research purposes is recommended to occur independently from the required clinical evaluation, as we will do in the proposed study. Nevertheless, studies focusing on the relationship between specific diagnoses and postoperative outcomes may fail to account for other psychological constructs that may be shared across diagnoses. Mood disorders, BED, and SUDs all share the common psychological construct of impulsivity, considered an important aspect of executive functioning. A lack of impulse control may contribute to the excessive weight gain seen in extreme obesity and may impact the results of bariatric surgery. Disinhibition and Impulsivity among Persons with Extreme Obesity Studies have suggested that individuals with obesity, and in particular those with extreme obesity presenting for bariatric surgery, show some deficits in executive functioning. For example, candidates for bariatric surgery have shown deficits in working memory, mental flexibility, motor speed and complex attention.57,58 These deficits could impact comprehension and retention of information presented to patients during the preoperative consultation process and, thus, negatively impact the ability to adhere to the dietary and behavioral changes required for an optimal postoperative outcome.45 At the same time, metabolic dysregulation, such as insulin resistance or hyperglycemeia seen in type 2 diabetes, also is associated with cognitive deficits, suggesting a potential physiological mechanism for the relationship.59-61 Dietary disinhibition, defined as a loss of control over eating, plays a central role in the overconsumption of food and, subsequently, the development of obesity.62.63 Disinhibition is similar to impulsivity, the term more commonly used in the substance use and smoking cessation literatures. Impulsivity is a multi-faceted construct and refers to the absence of the ability to inhibit an automatic behavior (otherwise known as response inhibition)64,65 and the tendency to discount future consequences in favor of more immediate outcomes (known as delay discounting).66,67 Similar to the role of disinhibition in obesity, impulsivity contributes to the development of and relapse with SUDs. Indeed, response inhibition and delay discounting are associated with both SUDs68-70 and obesity.71,72 Both also predict response to treatment for both SUDs73-75 and obesity.76 Chronic overeating and binge eating share several neurobiological and behavioral similarities with SUDs.77,78 In this regard, both may be viewed as behavioral disorders, in which intake (of food, alcohol, and/or drugs) escalates to a rate that is unhealthy and maladaptive. Nevertheless, the specific nature of the relationship between binge eating and substance use remains to be fully elucidated.79 There are similarities between binge eating and addictive disorders, including craving for the desired substance (drug or highly palatable food), a sense of loss of control when using, repeated attempts to control use despite clear adverse consequences, and the dedication of much time in obtaining and using the substance.80-82 Thus, the disinhibition observed with obesity and binge eating, the impulsivity seen with substance use disorders, and the emotional dysregulation associated with mood disorders all likely share commonalities (dashed lines in Figure 1) that may both contribute to the development of extreme obesity and also may be associated with weight loss (solid lines in Figure 1) and changes in psychosocial status after bariatric surgery. Psychosocial Status and Psychopathology after Bariatric Surgery In general, individuals who undergo bariatric surgery report dramatic improvements in psychosocial status and functioning postoperatively.83,84 The vast majority of patients report significant reductions in symptoms of depression and anxiety in the first postoperative year. They also report significant improvements in health and weight-related quality of life. Patients also report improvements in body image, sexual functioning, and relationship satisfaction.85-87 The relationship between preoperative psychopathology and postoperative outcomes is less robust.34,84 Livhits and colleagues reviewed this literature and concluded that the preoperative factors of BMI, BED, and the presence of personality disorders provided the strongest negative associations with postoperative weight loss.42 At least two studies have suggested that preoperative psychopathology, particularly mood and anxiety disorders, is associated with smaller weight postoperative weight losses.88,89 The relationship between BED and postoperative weight loss is unclear; some studies have found a relationship between preoperative BED and postoperative weight loss90.91 while others have not.92-94 Additionally, two studies have suggested that a history of substance abuse is associated with larger weight losses following bariatric surgery.95.96 The interpretation of this counterintuitive finding is that the selfregulation skills that help patients maintain their sobriety also help patients adhere to the demands of the recommended postoperative diet. Disinhibition and Impulsivity following Bariatric Surgery Encouragingly, studies have shown that there are improvements in executive functioning in persons with extreme obesity in the first two years after bariatric surgery.97,98 Postoperatively, patients typically report decreases in disinhibition and hunger, as well as increases in cognitive restraint.99,100 The physical aspects of bariatric surgery typically prevent individuals from eating the objectively large amount of food necessary to meet the diagnostic criteria of BED. However, many individuals continue to report the feeling of loss of control over their eating.44 The self-reported inability to control these impulses postoperatively is associated with smaller weight losses and greater emotional distress in the first few postoperative years.91,99,101,102 There is additional evidence that patients have difficulty with impulse control after surgery. A number of studies have suggested that there is an increased risk of substance abuse following bariatric surgery.101,103,104 King and colleagues,105 in their seminal investigation, found an increased rate of alcohol use disorder in the second postoperative year as compared to the year prior to surgery or in the first postoperative year. Other recent studies also have found increases in alcohol or composite substance abuse (drug, alcohol, or cigarettes) in the first two years after bariatric surgery.106-108 Postoperative substance use has been associated with smaller postoperative weight losses, postoperative nocturnal eating, and subjective hunger.109 Patients at

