
Characteristics of the Study Population

Target population

Adults aged 18-65 years old who plan to undergo one of two bariatric surgeries, either Rous-en-Y Gastric Bypass (RYGB) or Laparoscopic Sleeve Gastrectomy (LSG) at the University of Pennsylvania Health System. Based on our previous studies of bariatric surgery patients, we expect that approximately 80% of participants will be women and 20% of participants will be ethnic minorities.

Subjects enrolled by Penn Researchers 300

Subjects enrolled by Collaborating Researchers

0

Accrual

Participants will be recruited from the Bariatric Surgery Programs at the Hospital of the University of Pennsylvania and Presbyterian Medical Center, all part of Penn Medicine. We will enroll participants until a total of 300 adults have completed baseline visits. We anticipate that we will need to consent a larger number of participants in order to meet this enrollment goal. Based on our previous studies of bariatric surgery patients, we expect that approximately 80% of participants will be women and 20% of participants will be ethnic minorities. [name], Director of the Bariatric Surgery Program, conducts approximately 300 bariatric surgery operations per year. Additional surgeons in the Bariatric Surgery Program (at the Hospital of the University of Pennsylvania, Presbyterian Medical Center, and Pennsylvania Hospital) operate on approximately 200 patients per year. In order to increase the diversity and size of our sample, participants will also be recruited from the Temple Health Bariatric Surgery Program. The patient flow at Temple Health is similar to that of the Penn Health System (described below). Participants will be approached by the Research team during their pre-operative testing and education process.

Key inclusion criteria

We seek to enroll a sample of patients that is representative of those who present for bariatric surgery. We have based our exclusion criteria for the study largely on the clinical criteria used for bariatric surgery as well as our previous studies with bariatric patients. Inclusion Criteria: Adults aged 18-65 years old 18 years of age or above BMI of 35-60 kg/m2 (or 35 kg/m2 in the presence of significant weight-related comorbidities, including established coronary artery disease, established peripheral arterial disease, symptomatic carotid artery disease, sleep apnea, metabolic syndrome, cardiomyopathy, hypertension, and debilitating joint pain).

Key exclusion criteria

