
The following documents are currently attached to this item:

There are no documents attached for this item.

Deception

Does your project use deception? No

Analysis Plan

Analysis will be conducted using Stata 13.0 (Stata Corporation, College Station, TX). After the completion of quality assurance procedures, descriptive statistics will be summarized for all patients by predictor group (dichotomized). Data screening: Prior to performing analyses, standard data screening/ cleaning procedures will be applied. These procedures will: screen the data for data-entry errors; check for outliers; assess the extent and pattern of missing data; create all summary scores needed for analysis; and check that appropriate assumptions of normality are met. In all analyses, the assumptions underlying the application of all the statistical methods that are used will be examined, principally through the use of standardized residuals, influence diagnostics, and graphical displays. Image processing will include image quality assessment procedures that examine global and region of interest (ROI) based raw and processed temporal signal-to-noise ratio, absolute and relative motion, and signal spike count. Potential outliers will be identified in the cumulative sample by examining quality assessment measures and flagging for further investigation subjects greater than two standard deviations from the mean on any one measure (i.e., behavioral performance, image distortion and artifact, general linear model fit). The purpose of this evaluation is to determine whether the time series is likely valid, and, if so, it will remain. Otherwise it will be corrected, if feasible, or removed from the analysis. The final sample will be examined in a similar fashion to determine whether any subjects warrant data cleaning or require exclusion from the final statistical analysis. Analysis of repeated measures: Our four-session within-subject design will generate multiple outcome measures that belong to the Gaussian family, and we will therefore use standard repeated-measures analysis of variance (ANOVA). Imaging outcomes (perfusion and BOLD) will be modeled using standard voxel-based image analysis techniques (described below) that incorporate random effects. Other outcomes (weight loss, ratings) will be modeled using a linear mixed-effects models framework, using using Stata 13.0 (Stata Corporation, College Station, TX). We could use a population averaged approach such as generalized estimating equations. However, the mixed model approach will provide the flexibility to allow for different error variances for different sessions if necessary. Voxel-based image analysis has limited flexibility, particularly when adding multiple covariates and interaction. When needed, summary values (e.g., mean rCBF, mean BOLD% signal change) extracted from ROIs will be modeled in STATAs mixed-models framework. These models can be extended to include additional explanatory variables (e.g., weight change, heart rate, respirations, age). Primary Aim 1 We will take a mixed models approach. The main interest in this study is the Group x Time interaction, where Group will be a between-subjects factor and Time will be a categorical within-subjects factor. This can be interpreted as population averages (GEE fitting method). Hypothesis 1: We will fit a 2 (Group: Dichotomized Baseline Measures, Low, High) x 3 (Time: change from baseline to month 6, 12 and 24) mixed-effects model for change in weight. Hypothesis 2: We will fit a 2 (Group: Dichotomized difference scores, 6 Month minus Baseline, Low, High) x 2 (Time: change from baseline to months 12 and 24) mixedeffects model for change in weight. In addition, the mixed effects models will include adjustments for surgical procedure, gender, and time since surgery. We recognize that the change in weight could also be associated with effects of several pertinent patient characteristics. To this end, we will consider additional covariates (e.g. sociodemographic variables, comorbidities, medication use, tobacco use, and initial weight). For both hypotheses, we will explore the continuous version of our predictor variables, where in place of Group, we use the real values of the predictor. This yields a difference of slopes with respect to predictor value across time points. Secondary Aim 1 We will use confirmatory factor analysis to verify our expected natural groupings of individual measures into composite measures. We will specify 3 factors and use Varimax rotation. We will assemble composite scores for each of our constructs by summing the standardized score values. We will then standardize the composite score and outcome (change in weight at 24 months). We will estimate the partial correlations (direct and indirect) among individual measures, composites, and outcome in a path analysis as suggested by Figure 1 to estimate the fraction of variance in outcome accounted for by each of the constructs. Secondary Aim 2 The outcomes will consist of (continuous) changes in behavior from baseline. We will use correlation to examine the relationship of baseline impulsivity measures to changes at 6, 12 and 24 months. The exception is changes in diet composition. In this analysis, we will use multivariate regression methods,

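### No analysis commits to an age term for the reaction-time impulsivity scores in an 18-65 cohort, so their associations with outcome could be biased by age in either direction

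*Combined protocol and SAP*

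**What the plan says.** **Scores.** Study Instruments, repeated under Procedures, defines stop signal reaction time (SSRT) as mean go-trial reaction time minus mean stop delay. Stroop interference is incongruent minus congruent reaction time. The third measure, the delay discount rate k, is not a reaction time. The impulsivity composite is formed by "averaging individual z-scores derived from the SST, Stroop interference score, and k-value". No age norms or age-adjusted z-scores are described.

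**Prediction.** Worse scores ("slower SST, higher Stroop interference score, and higher k-values) will be associated with less weight loss 24 months following bariatric surgery") are taken to indicate greater impulsivity.

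**Population.** Key inclusion criteria state "Adults aged 18-65 years old". The study is observational, with no randomization.

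**Primary Aim 1.** The Analysis Plan says "the mixed effects models will include adjustments for surgical procedure, gender, and time since surgery". Further covariates will only be considered, with sociodemographic variables and comorbidities among the examples. Age is named once in the plan, in the general modelling and imaging text, as an example of a variable by which models can be extended.

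**Secondary Aim 2.** "We will use correlation to examine the relationship of baseline impulsivity measures to changes at 6, 12 and 24 months". Apart from a separate regression approach for diet composition, no adjustment is named.

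**The concern.** Without randomization, the choice of covariates carries the inference. A reaction-time score can vary with age for reasons unrelated to impulsivity. If age is also related to weight change or to the behavioural outcomes, an unadjusted association between score and outcome contains an age component.

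Objective impulse-control testing is the gap that the Background says this study fills, so these are the associations readers will look at first. Primary Aim 1 leaves the adjustment optional, so it could be chosen after the results are seen. In Secondary Aim 2 the stated method is itself unadjusted. The plan fixes gender and gives no reason for not fixing age.

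**Working it through.** **Inputs from the documents.** N = 300 completed baseline visits (Accrual); age range, score definitions and models as above. The objectives say the study is powered on Specific Aim 1, but the text available gives no alpha, power, effect size, SD or dropout. There is therefore no stated figure to reproduce.

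**Assumed inputs.** Two-sided alpha of 5%; no true association between score and outcome at a given age; correlation of age with the score a = 0.2 to 0.4; correlation of age with the outcome b = 0.1 to 0.2 in absolute value. The sign of b is open.

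**Step 1: induced correlation.** With no true association at a given age, r = a x b.

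**Step 2: continuous correlation.** This is the form of test in Secondary Aim 2. By Fisher z, the mean shift is m = atanh(r) x sqrt(300 - 3). The rejection rate is [1 - Phi(1.96 - m)] + Phi(-1.96 - m).

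**Step 3: simple low/high comparison, 150 per group.** A median split reduces the correlation to r' = r x sqrt(2/pi). Then d = 2r'/sqrt(1 - r'^2), and the shift is d/sqrt(2/150).

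| a, b | r | m | Rejects, continuous | d | Rejects, low/high |
|---|---|---|---|---|---|
| 0.2, 0.1 | 0.020 | 0.345 | 6.4% | 0.032 | 5.9% |
| 0.3, 0.15 | 0.045 | 0.776 | 12.1% | 0.072 | 9.5% |
| 0.4, 0.2 | 0.080 | 1.382 | 28.2% | 0.128 | 19.8% |

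If a or b is zero, then r = 0 and the rate is 5%. With 240 patients analysed (an assumed 20% loss), the continuous rates at the two ends are 6.1% and 23.5%.

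**Step 4: direction.** If older patients do worse, the share of rejections that fall in the predicted direction is [1 - Phi(1.96 - m)] divided by the rejection rate: 83%, 97% and over 99% in the three rows. If older patients do better, the induced correlation has the opposite sign and would mask a true association.

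**Step 5: effect of adjusting.** In a simulation (2,000 runs, age uniform on 18-65, n = 300) with a = 0.3 and b = -0.2, the false-positive rate was 18.8% without age and 4.7% with it. The formula gives 17.9% for the unadjusted case. With a = 0.3 and b = 0 the rates were 5.2% and 5.3%.

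**Step 6: the Group x Time test.** Let the age effect on weight change at visit t be b_t. The Group x Time contrast between visits s and t is then biased by (b_t - b_s) times the mean age difference between the High and Low groups. If the age effect is the same at months 6, 12 and 24, this is zero. Simulation agrees: about 5% with a constant age effect. Where the age effect was assumed to grow over time, the rate was about 11-15% in the cases tried, and about 5% again with an age x time term. The 11-15% is illustrative and not a bound: it depends strongly on the assumed growth and on the correlation between visits, and the documents give neither.

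**The case against.** **Age is not absent.** A reader might infer that the plan ignores age. It does not: age is named as a possible extension and is implied by sociodemographic variables. The gap is between optional and committed for Primary Aim 1, and an unadjusted method for Secondary Aim 2.

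**The mechanism is assumed.** A reader might infer that ordinary slowing with age will produce the predicted result. The documents give neither the link of age with the scores nor the link of age with outcome, and the Background's summary of the strongest negative preoperative factors does not list age. This stands: size and sign are open, and the bias could run either way.

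**The primary test is less exposed.** The main interest in Primary Aim 1 is Group x Time, which a constant age effect does not touch. This stands, and it is why the 6-28% range must not be read as the error rate of the primary test. Hypothesis 2 uses within-person six-month changes, in which stable age differences largely cancel.

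**The scoring handles part of it.** The protocol notes that the Stroop difference allows for overall naming speed, and the stop-delay staircase follows go speed. Subtraction removes additive slowing but not proportional slowing: with 20% slowing, an illustrative 100 ms interference becomes 120 ms. SSRT is itself a latency, so slower stopping with age would remain. The objection reduces the problem without removing it.

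**Wider claims.** A reader might extend the point to the Secondary Aim 1 path analysis, to the discount rate or to diabetes. The path model rests on a figure not shown, so the absence of covariates there cannot be confirmed. The discount rate is not a reaction time. The Background says "metabolic dysregulation, such as insulin resistance or hyperglycemeia seen in type 2 diabetes, also is associated with cognitive deficits" and presents this as a possible mechanism, so adjusting for diabetes could remove signal of interest. None of these belongs in the point.

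**Conclusion.** The point holds in a limited form. SSRT and Stroop interference are unadjusted reaction-time scores across a wide age range, and no analysis is committed to an age term. Whether this distorts the results depends on two links that the documents do not give. Under the assumed ranges, the false-positive rate is about 6-28% for a continuous correlation and about 6-20% for a simple low/high comparison. Group x Time is affected only if the age effect changes over follow-up.

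The documents do not support saying that a positive impulsivity result could not be told apart from an age effect: age can be added to the models, and the plan contemplates adding it. Nor do they support a claim that false positives would nearly always fall in the predicted direction. That needs older patients to do worse, and even then the share is 83% at the low end. The point is worth acting on because the remedy is nearly free and removes a choice that could otherwise be made after seeing the data.

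**What to change.** In the Analysis Plan:

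- **Primary Aim 1, Hypothesis 1.** For every model with an impulsivity predictor, dichotomized or continuous, list baseline age (continuous) and age x time as fixed covariates alongside surgical procedure, gender and time since surgery.
- **Secondary Aim 2.** Replace the plain correlations for baseline impulsivity with partial correlations adjusted for baseline age.

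Hypothesis 2, the composite, the discount rate and diabetes status need no change on this ground.

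**Cost.** SAP wording only, with no new data or visits and no change in sample size. Age with a three-level time factor uses 1 + 2 = 3 degrees of freedom in the Hypothesis 1 models; each partial correlation uses one.
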